permanent treatment interruption in eight patients (5%), which happened in the first 26 months. With crizotinib, 15% of patients had dose reduction, 48% had temporary treatment interruption, and 11% had permanent discontinuation because of AEs from any cause.

Solomon et al reported lorlatinib is associated with neurologic toxicity (mood/speech and cognitive areas), accounting for 35% of patients in the CROWN trial (3yr follow up of the pivotal trial⁸), being in most patients grade 1. CNS AEs did not have a negative impact on patient-reported quality of life. Most CNS AEs resolved (33% without intervention and 17% with lorlatinib dose modification), while 38% were unresolved; most required no intervention. Lorlatinib dose modification did not influence PFS. Few observational studies have reported the frequency of CNS toxicity on patients with ALK+ NSCLC receiving lorlatinib, however no information is available regarding patients from South Europe. The study will be relevant to learn more about the frequency in our population and about the clinical management in real clinical practice.

Lorlatinib also had a manageable safety profile, with hyperlipidemia, weight gain, and hypertension being the most common G3/4 adverse events and some others with lower frequency as the alterations at the CNS level (mood/speech and cognitive) that generate some uncertainties regarding an adequate management. Occurrence of adverse events with lorlatinib in Spain (2nd and later lines approval in February 2021) is known in later lines of treatment and it seems that several factors involved in that previously treated population (use of radiotherapy, presence/absence of baseline intracranial metastasis, use of concomitant drugs, personal clinical history of psychiatric/mood diseases, etc.) are associated to certain types of AEs, i.e. the CNS adverse events⁶, but the occurrence of those AEs are not well-known with the use of the drug in the first line of treatment (local approval February 2023) and that is one of the reasons why this data gap with lorlatinib should be covered.

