2. rwDuration of Response (DoR)	2. To determine real world duration of response (DOR), as the time from the first occurrence of a documented objective response to disease progression or death from any cause, whichever occurs first, as determined by the investigator according to RECIST v1.1. criteria (or Time from first documentation of CR or PR (whichever occurs first) after index until death or PD)			
3. rwDuration of Treatment (DoT)	3. To determine duration of treatment (DoT) as the time from lorlatinib's first dose to last dose for any cause. (Time to treatment discontinuation or Time from first dose to last dose of a treatment)			

4.	rwTime to next therapy/treatment (TTNT)	4.	To determine Time to next therapy/treatment (TTNT) as the Time from end of lorlatinib treatment to institution of next therapy	
5.	rwSystemic and intracranial Objective Response rate (ORR) using RECIST v1.1. criteria.	5.	To determine the systemic and real-world intracranial objective response rate (ORR) as determined by the investigator using RECIST v1.1. criteria	
6.	rwTime to intracranial progression rate at 12 and 18 months with and without brain metastasis at baseline	6.	Real world Time to intracranial progression rate at 12 and 18 months with and without brain metastasis at baseline	
7.	rwCumulative incidence of brain metastases (BM) in ITT population at 12 and 18 months (with and without baseline BM)	7.	Real world Cumulative incidence of brain metastases (BM) in ITT population at 12 and 18 months (with and without baseline BM)	
8.	rwOverall survival (OS) rate at 12 and 18m	8.	To determine the real-world overall survival (OS) rate at 12 and 18 months. OS is defined as the time from enrollment to death from any cause	
To evaluate the impact of lorlatinib on patients' quality of life.		of Pl Lo ar	hange from baseline in health-related quality f life (HRQoL), using the EORTC C30, RO_CTCAE (for CNS AEs) and submodules C13 at baseline, C1D15, C2D1, C3D1, C6D1 and every 3 months until the 1st year and then very 6 months	
To describe ALK testing methods used		Describe the different methods used to testing ALK mutations		
Exploratory Objectives (up to 30 patients)			Corresponding Endpoints	
To identify neuroimaging markers (MRI) that are predictive of the occurrence of CNS AEs		Fazekas scale, morphometric and radiomic analysis of baseline magnetic resonance images (MRIs) to identify imaging markers associated with the development of CNS AEs		

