- 1. **Baseline visit:** the day on which the patient fulfils the inclusion and exclusion criterion, including signature of the Informed Consent (i.e. the day on which the prospective observation starts) (within cycle 1 if lorlatinib)
- 2. Follow-up visit 1: will be scheduled at month 3 (third cycle of Iorlatinib)
- 3. Follow-up visit 2: will be scheduled at month 6 (sixth cycle of Iorlatinib)
- 4. Follow-up visit 3: Follow-up visit at month 12 (twelfth cycle of lorlatinib)
- 5. Final Visit: end of follow-up (end of data collection expected November 2027)

Data collection overview

Study Visits and Assessments	Baseline			FU3 C12D1	Final Visit
Informed consent	X				
SOCIO DEMOGRAPHIC DATA					
Medical history	X				
Physical examination including Height and weight	X	X	X	X	X

Study Visits and Assessments	Baseline	FU1	FU2	FU3	Final
		C3D1	C6D1	C12D1	Visit
Previous personal and family history of cancer	X				
CLINICAL DATA					
ECOG	X	X	X	X	X
Laboratory: Hematology and Blood chemistry (dyslipemia profile included). According to routine clinical practice	X	X	X	X	X
Comorbidities since Index Date: Charlson Index	X	X	X	X	X
Concomitant treatment(s) including previous history of Thromboembolic Disease	X	Х	X	X	X
Information of baseline tumor diagnosis: date, staging, (TNM),biopsy, PD-L1 expression, other mutations, etc	X				
Information regarding advanced disease: date, staging, metastatic location, CNS metastasis, previous systemic chemotherapy, radiotherapy, etc	X				
Previous systemic chemotherapy (Yes/No)	X				
Assessments CT scan	X				
Assessments brain MRI	X				
LORLATINIB TREATMENT					
Start, Stop and Discontinuation date	X	X	X	X	X
Dose by cycle	X	X	X	X	X
Reason for discontinuation or for dose reduction	X	X	X	X	X
Evaluation of Treatment Response: method (CT scan, MRI, others) and response	х	Х	X	X	X
AFTER LORLATINIB TREATMENT					

Study Visits and Assessments		FU1	FU2	FU3	Final
		C3D1	C6D1	C12D1	Visit
Post-progression treatment: type and palliative care					X
Date of death or last follow-up or last contact					X
QUALITY OF LIVE					
EORTC QLQ C30, LC13	X	X	X	X	X
SAFETY					
PRO-CTCAE	X	X	X	X	X
Adverse Events	X	X	X	X	X

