Imaging method for brain metastasis screening	patient's characteristics	Investigators Patient clinical record/Electronic Health record (EHR)	• (CT/MRI/None/Unknown)
Brain metastases present at time of lorlatinib initiation	patient's characteristics	Investigators Patient clinical record/Electronic Health record (EHR)	• Yes/No
Previous treatments for brain metastasis	patient's characteristics	Investigators Patient clinical record/Electronic Health record (EHR)	 Concomitant steroid treatment (Yes/No) Symptomatic (Yes/No) List

Variable	Role	Data source(s)	Operational definition
Surgery	Baseline patient's characteristics	Investigators Patient clinical record/Electronic Health record (EHR)	Yes/No. Date
Whole brain radiation Yes/No (Date of last dose)	Baseline patient's characteristics	Investigators Patient clinical record/Electronic Health record (EHR)	• (Date of last dose)
SRS/radiosurgery	Baseline patient's characteristics	Investigators Patient clinical record/Electronic Health record (EHR)	Yes/No (Date of last dose
Has the patient participated in a clinical trial previously?	Baseline patient's characteristics	Investigators Patient clinical record/Electronic Health record (EHR)	• (Yes/No/Unknown)
Previous radiotherapy	Baseline patient's characteristics	Investigators Patient clinical record/Electronic Health record (EHR)	• (Yes/No)
Intention of previous radiotherapy	Baseline patient's characteristics	Investigators Patient clinical record/Electronic Health record (EHR)	Curative, palliative

Variable	Role	Data source(s)	C	perational definition
Location of previous curative radiotherapy	Baseline patient's characteristics	Investigators Patient clinical record/Electronic Health record (EHR)	•	Chest, bone, brain, others (specify
Previous systemic chemotherapy	Baseline patient's characteristics	Investigators Patient clinical record/Electronic Health record (EHR)	•	Yes/No
Previous systemic chemotherapy Intention	Baseline patient's characteristics	Investigators Patient clinical record/Electronic Health record (EHR)	•	Curative (adjuvant or neoadjuvant)
Previous systemic chemotherapy Regimen used	Baseline patient's characteristics	Investigators Patient clinical record/Electronic Health record (EHR)	•	List
Clinical data during t	reatment with le	orlatinib		
Start and end of treatment	notiont's	Investigators Patient clinical record/Electronic Health record (EHR)	•	Date from the first lorlatinib treatment taken and last

Variable	Role	Data source(s)	Operational definition

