Starting dose	patient's characteristics	Investigators Patient clinical record/Electronic Health record (EHR)	• mg
Dose Reduction	notiont's	Investigators Patient clinical record/Electronic Health record (EHR)	 (Yes / no) Date Reason
Any other mitigation strategies?	notiont's	Investigators Patient clinical record/Electronic Health record (EHR)	 Minimum dose reached Was the dose increased following a dose reduction? Yes/No Specify
Temporary interruption of treatment	patient's	Investigators Patient clinical record/Electronic Health record (EHR)	 (Yes / No) Reason for discontinuation of treatment: progression, toxicity, others
Interruption time (in days)	patient's characteristics	Investigators Patient clinical record/Electronic Health record (EHR)	• Days
Date of progression to treatment	patient's characteristics	Investigators Patient clinical record/Electronic Health record (EHR)	Date of progression to treatment
Treatment after progression	patient's	Investigators Patient clinical record/Electronic	• (Yes / No).

Variable	Role	Data source(s)	Or	oerational definition
		Health record (EHR)		Date of definitive discontinuation of treatment
Best tumor response	patient's	Investigators Patient clinical record/Electronic Health record (EHR)		(Complete response / Partial response / Stable disease / Progression)
Height at maximum tumor response	patient's	Investigators Patient clinical record/Electronic Health record (EHR)	• ;	Meters
Weight at maximum tumor response	patient's characteristics	Investigators Patient clinical record/Electronic Health record (EHR)	•]	kg
In case of CNS disease: Response in CNS	notiont's	Investigators Patient clinical record/Electronic Health record (EHR)		(Yes / No / Not documented-evaluable)
Brain progression	patient's	Investigators Patient clinical record/Electronic Health record (EHR)	•	Yes/No
Tumor progression location (select all that apply)	patient's characteristics	Investigators Patient clinical record/Electronic Health record (EHR)	• :	Lung Brain Liver Renal Other (specify)

Variable	Role	Data source(s)	Operational definition
Re-biopsy at tumor progression	patient's	Investigators Patient clinical record/Electronic Health record (EHR)	• Yes/No
Liquid biopsy performed at progression	patient's	Investigators Patient clinical record/Electronic Health record (EHR)	• Yes/No
Performance status at the time of progression	notiont's	Investigators Patient clinical record/Electronic Health record (EHR)	Autonomy Status (patient) by ECOG categories

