Height at tumor progression	patient's characteristics	Investigators Patient clinical record/Electronic Health record (EHR)	• Meters
Weight at tumor progression	patient's	Investigators Patient clinical record/Electronic Health record (EHR)	• kg
Post-progression treatment	patient s	Investigators Patient clinical record/Electronic Health record (EHR)	• Yes/No
Post progression treatment Type	patient's characteristics	Investigators Patient clinical record/Electronic	Chemotherapy, TKI (specify type), Immunotherapy,

Variable	Role	Data source(s)	Operational definition
		Health record (EHR)	Radiotherapy, Palliative Care.
Post progression treatments	On-treatment patient's characteristics		Describe subsequent treatment
Clinical data after lorlatinib completion			
Alive: Yes/No	After- treatment data	Investigators Patient clinical record/Electronic Health record (EHR)	• Yes/No
Date of death or last follow-up	After- treatment data	Investigators Patient clinical record/Electronic Health record (EHR)	Date format

Variable	Role	Data source(s)	Operational definition
Participant's perspective			
EORTC QLQ-C30	Outcome measure	Baseline, C3D1, C6D1, C12D1, Final visit	ePRO (through mobile device) questionnaire containing 30 questions and assesses the quality of life of oncological participants multidimensionally over 10 subscales.
EORTC QLQ-LC13	Outcome measure	Baseline, C3D1, C6D1, C12D1, Final visit	ePRO (through mobile device) questionnaire for lung participants. The QLQ-LC13 incorporates one multi-item scale to assess lung cancerassociated symptoms (i.e.coughing, haemoptysis, dyspnoea and pain) and side- effects from conventional chemo- and radiotherapy.
PRO-CTCAE (only for CNS AEs)	Outcome measure	Baseline, C3D1, C6D1, C12D1, Final visit	ePRO (through mobile device) questionnaire. When referring to CNS (Central Nervous System) adverse events, the PRO-CTCAE helps in assessing symptoms such as headaches, dizziness, and cognitive changes, which are crucial for understanding the impact of cancer treatments on the nervous system.

Variable	Role	Data source(s)	Operational definition
Exploratory variables (30 patients expected)			
To identify neuroimaging markers (MRI) that are predictive of the occurrence of CNS AEs	Exploratory analysis	MRI	Fazekas scale, morphometric and radiomic analysis of baseline magnetic resonance images (MRIs) to identify imaging markers associated with the development of CNS AEs.

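### Section 9.3 has no dedicated field for local brain treatment given between lorlatinib start and progression, so the intracranial endpoints may include an effect that cannot be identified afterwards

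*Protocol*

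**What the plan says.** All references are to the protocol.

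- **Before lorlatinib (Section 9.3).** Under "Previous treatments for brain metastasis" come surgery, radiosurgery and the item "Whole brain radiation Yes/No (Date of last dose", each with a date and the role of a baseline characteristic. The general radiotherapy items are also worded as previous treatment. Brain is one of the sites offered under "Location of previous curative radiotherapy".
- **On lorlatinib (Section 9.3).** The block covers dose, dose reduction, other mitigation, interruption, response and progression. CNS response is a single item, "In case of CNS disease: Response in CNS", answered yes, no, or not documented/evaluable. There is no item for radiotherapy or surgery.
- **After progression (Section 9.3).** Radiotherapy reappears as one option under "Post progression treatment Type".
- **Visit table (Section 9.2).** The row containing "metastatic location, CNS metastasis, previous systemic chemotherapy, radiotherapy, etc" is marked at baseline only. Post-progression treatment is marked at the final visit only. A general row for concomitant treatments is marked at all five visits, with no further specification.
- **Endpoints (Section 9.1).** Item 5 reads "To determine the systemic and real-world intracranial objective response rate (ORR) as determined by the investigator using RECIST v1.1. criteria". Item 6 is time to intracranial progression at 12 and 18 months, with and without baseline brain metastases. Neither mentions local brain treatment.

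**The concern.** Intracranial disease is allowed by inclusion criterion 3, and the baseline variables foresee symptomatic and steroid-treated brain metastases. These are patients in whom radiosurgery or surgery during lorlatinib treatment, without progression, is plausible. Such treatment can shrink a lesion or delay its regrowth. If it is not recorded in a usable form, an intracranial response or a longer time to intracranial progression is reported as an outcome of first-line lorlatinib, and nobody can later separate the two contributions. The expected direction favours the drug.

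Intracranial ORR and time to intracranial progression are two of the eight listed effectiveness outcomes. The primary objective, describing adverse events, is not altered.

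**Working it through.** The protocol states no figure on this point, so the check is a reading of the variables against the timeline, followed by an illustration of scale.

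**Step 1. Follow local brain treatment through the study periods.**

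| Time of treatment | Where it would be recorded | Type and date specified? |
|---|---|---|
| Before first dose | Baseline brain-treatment items, Section 9.3 | Yes |
| After first dose, before enrolment (7 to 28 days later) | Unclear: the block heading and the pre-index definition in Section 9.2 stop at lorlatinib start, but the items are dated and completed at enrolment | Possibly, through the date |
| After enrolment, before progression | Only the general concomitant-treatments row, Section 9.2 | No |
| After progression | Post-progression treatment type, Section 9.3 | Type, yes |

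The third line is the gap; the second is an ambiguity. In Section 9.3 the nearest counterpart to the concomitant-treatments row is a baseline item on concurrent medications (neurotropic, psychiatric and mood drugs, anticonvulsants, other). That item does not define the all-visit row, but nothing else says that the row should hold radiotherapy or surgery. A blank there could not be read as no local treatment given.

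**Step 2. Can this be left to the statistical analysis plan?** Section 9.7 assigns outcome definitions and censoring methods to that plan. A plan can only censor at, or describe, an event whose date is in the database. The text after the Section 9.3 table limits documentation to routine-practice variables that follow the objectives. An item left out there is unlikely to be in the eCRF. The data-capture part therefore belongs to the protocol.

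**Step 3. Scale.** Inputs: 35 lorlatinib patients with baseline brain metastases and 149 lorlatinib-treated patients in the pivotal trial (Section 7), and planned N = 116 (Section 9.5). Assumption: the pivotal trial's share applies here.

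- Share: 35 / 149 = 23.5%.
- Expected patients with baseline brain metastases: 116 × 35 / 149 = 27.2, about 27.
- Effect of one response due to local treatment rather than lorlatinib: 1 / 27 = 3.7 percentage points of intracranial ORR.
- Two such responses: 2 / 27 = 7.4 points.

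These are upper values. A locally treated patient who would have responded to lorlatinib anyway moves the rate by nothing.

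**The case against.** The strongest reply is that the plan already has somewhere to put this information. The concomitant-treatments row refers to treatments and is marked at every visit, so radiosurgery at month 6 could be entered there. The baseline brain items carry dates and are completed 7 to 28 days after first dose, so radiosurgery on day 12 could be visible from its date. An investigator may also answer not documented/evaluable for CNS response in a treated lesion. All of this stands. It rules out saying that such treatment has no place in the data or is necessarily lost. It does not make capture systematic.

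It is also fair that, in a single-arm descriptive study of routine care, an as-observed intracranial result that includes local treatment is a legitimate quantity. Discounting treated lesions in the main result would be a choice of estimand, not a correction of an error.

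A reader might infer three stronger things that the protocol does not support.

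- **That the CNS adverse event predictor is misclassified.** Section 7 lists "use of radiotherapy, presence/absence of baseline intracranial metastasis, use of concomitant drugs" among the associated factors, but for a previously treated population, and the Abstract (Section 4) gives the factor as brain radiotherapy received earlier. A patient first irradiated on lorlatinib is correctly classed as having no prior brain radiotherapy. Radiotherapy given after a CNS event cannot predict it.
- **That radiation-related events are automatically attributed to lorlatinib.** Section 11 requires the investigator to assess and record causality for each safety event.
- **That intracranial ORR is inflated by 11 to 19 points.** This takes 10 to 20% of the 27 patients as locally treated (3 / 27 = 11.1; 5 / 27 = 18.5) and counts every one as a false response. The rate has no source in the protocol, so the figure is a ceiling on an unsupported assumption.

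**Conclusion.** The point holds as a gap in data capture. No dedicated variable covers local brain treatment between lorlatinib start and progression, and the only all-visit row that could catch it specifies no type, site or date. Intracranial ORR and time to intracranial progression may therefore include an effect of local treatment that cannot be identified, in lorlatinib's favour.

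The size per patient is up to 3.7 points of intracranial ORR, if about 27 of 116 patients have baseline brain metastases and all of them form the denominator. The total is unknown because the protocol gives no frequency. No bias is shown for prior brain radiotherapy as a predictor of CNS adverse events. At most, a description of on-treatment brain radiotherapy is missing. This is a cheap improvement worth making, not a flaw that invalidates an endpoint.

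**What to change.** 1. In Section 9.3, add local CNS therapy to the on-treatment variables: type (radiosurgery, whole-brain radiation, surgery), date, lesions treated and reason. Add the same item to every follow-up column of the visit table in Section 9.2, with an explicit answer for none given.
2. State that the dates in the baseline brain-treatment fields are used to separate treatment before the index date from treatment after it.
3. Report intracranial ORR and intracranial progression as observed. Beside them, give a supplementary analysis that censors progression at local CNS therapy given without progression, and does not count response in lesions so treated.
4. In the CNS adverse event predictor analysis, keep prior brain radiotherapy as the baseline factor. Describe separately any on-treatment brain radiotherapy that preceded a CNS event.

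The cost is a few eCRF fields and short text on endpoint handling. The item records what routine care already did, so the study stays non-interventional. The supplementary intracranial figure will be slightly lower and less precise than the as-observed one. If the fields are not added at the start, recovering the information would mean going back to charts at about 20 sites.

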radiotherapy, presence/absence of baseline intracranial metastasis, use of concomitant drugs, or personal clinical history of psychiatric/mood diseases⁶. However, limited data are available about the occurrence of CNS AEs when lorlatinib is used in the first line of treatment (local approval in Spain February 2023) in a real-world population.

On the other hand, lorlatinib has proved its efficacy and safety in clinical trials, but real-world evidence is needed to confirm these results in wider patient populations and to identify prognostic and predictive factors not captured in clinical trials. Ethnicity, molecular variants, and circulating tumour DNA (ctDNA) clearance may influence treatment outcomes and require personalized or combinational approaches.

Research question and objectives

Research question

 What is the spectrum of adverse events and mitigation strategies associated with lorlatinib as a first line treatment in an ALK+ NSCLC real-world Spanish population?

Primary Objective

 To describe all the spectrum of the adverse events (AEs) of Lorlatinib (CTCAE v6.0) and its mitigation strategies, with special interest in CNS AEs

Secondary Objectives

- To identify factors that are predictive of AEs, with special interest in CNS AEs
- To evaluate the effectiveness of 1L lorlatinib in real-world practice
 - 1. rwPFS rate at 12 and 18 months in the ITT population with and without brain metastasis at baseline
 - 2. rwDuration of Response (DoR)
 - 3. rwDuration of Treatment (DoT)
 - 4. rwTime to next therapy/treatment (TTNT)
 - 5. rwSystemic and intracranial Objective Response rate (ORR) using Response Evaluation Criteria in Solid Tumors (RECIST) v1.1. criteria
 - 6. rwTime to intracranial progression rate at 12 and 18 months with and without brain metastasis at baseline
 - 7. rwCumulative incidence of brain metastases (BM) in ITT population at 12 and 18 months (with and without baseline BM)

- 8. rwOverall survival (OS) rate at 12 and 18m
- To evaluate the impact of lorlatinib on patients' quality of life
- To describe ALK testing methods used

Exploratory Objectives (up to 30 patients)

 To identify neuroimaging markers (Magnetic Resonance Imaging; MRI) that are predictive of the occurrence of CNS AEs

Study Design

The study is an observational, non-interventional, prospective and multicenter trial that evaluates the real-world safety and effectiveness of lorlatinib as a first-line treatment in patients with ALK-positive advanced NSCLC in Spain.

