The investigators will collect the data of the patients included in an electronic data collection form (e-CRF) designed specifically for this study and developed by the CRO in charge at the beginning of the study. The data will be stored in an access database protected by password and only accessible to authorized personnel. Descriptive and survival analyses will be performed to evaluate the study objectives, using the Kaplan-Meier method and the Cox model. The AEs will be summarized by presenting the frequency distribution and percentage of these in the total number of patients and will be coded according to the CTCAE v6.0.

Imaging data^{9,10}

Brain MRI will be collected at baseline and in case of CNS toxicity. Images will be anonymized and centrally analyzed (See Section 9.3.7) to assess Fazekas scale, morphometric and radiomic features that will be correlated with CNS toxicity.

Baseline CT scan will be collected to determine the body composition. Images will be anonymized and centrally analyzed to assess radiomic features that will be correlated with CNS toxicity. Baseline body CT scan and brain MRI and first tumor assessment will be collected to determine body composition and to compare radiomic characteristics in patients who developed CNS AEs with those who did not.

Study size

In the CROWN trial, the incidence of CNS AEs was 42% and we assumed that the incidence could be higher in the real clinical practice, but it is probably under detected or recorded as most cases are grade 1. We estimated that we need 116 patients treated with lorlatinib in first-line therapy for ALK+ non-small cell lung cancer with an 80% power to detect an incidence of 55% any grade CNS AEs using a 2-sided test.

Data analysis

The safety assessment will be based primarily on the frequency and severity of AE. AEs will be summarized by presenting the number and percentage of these figures in the total number of patients. The absolute and variable frequencies of each AE with respect to the total number of reported AEs will also be presented. Descriptive analyses will be carried out to evaluate the objectives of the study.

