The study will capture results/data only from procedures that were actually performed as part of a participant's routine medical care, as determined by their treating physician.

Imaging analysis^{12,13}

Brain MRI will be collected at baseline and in case of CNS toxicity. Images will be anonymized and shared to assess Fazekas scale, morphometric and radiomic features that will be correlated with CNS toxicity.

The Fazekas scale will be calculated from the baseline MRI images of each patient. We will qualitatively evaluate the presence of White Matter hyperintensities on FLAIR images using a 4-point rating scale. Specifically, the assigned values for this rating scale were: 0 for no lesions, 1 for focal lesions, 2 for beginning confluence of lesions, and 3 for diffuse involvement of the entire regions with or without the involvement of U fibers.

The morphometric analysis will be completed by studying the volumetry of brain structures, including gray matter, white matter, and cerebrospinal fluid, which will also allow us to define the total intracranial volume. The morphometric analysis will be conducted using the SPM12 software (Welcome Department of Imaging Neuroscience Group) running on MATLAB (Mathworks). In patients with brain metastases at baseline, each of the lesions will be identified and delineated using T1-gadolinium and FLAIR (fluid-attenuated inversion recovery) utilizing the image analysis sequences, free software **MRIcron** (http://www.mccauslandcenter.sc.edu/mricron/mricron). The contrast-enhancing identified in the T1-gadolinium sequence will be defined as the tumor masks (ROI - region of interest). Similarly, the areas outlined in the FLAIR sequence will define the tumor edema compartment. In an initial analysis, the number of lesions, volumetric data (mm³) for each lesion, and the total sum of all lesions per patient will be calculated, as well as the tumor/edema ratio for each lesion and the sum of all lesions. We will perform an exploratory radiomics analysis, leveraging the masks (ROIs) previously defined in the morphometric analysis. After delineating the ROIs in the previous analysis, several variables related to texture and edge descriptors will be extracted. Weighted averages of each radiomics variable will be obtained for patients with more than one metastatic lesion. These averages will be weighted by the volume of the metastasis. All these parameters will be correlated with the CNS toxicity.

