Baseline CT scan will be collected to determine the body composition. Images will be anonymized and shared to assess radiomic features that will be correlated with CNS toxicity.

Central Review

All brain MRIs will be centrally reviewed in Anonymized images with an adequate resolution level that allow for a centralized reading directly on the images, will be collected in a specific platform where the centralized reading will be conducted by central reviewer through a controlled access to the platform and complying with all the current legal requirements regarding data protection.

Central reviewer:

[name]

Department of Medical Oncology

ICO Hospitalet, Barcelona (Spain)

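### Baseline brain MRIs and toxicity-triggered MRIs go to the same central review, with no masking to CNS adverse events and no reading order stated

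*Protocol*

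**What the plan says.** Section 9.3 (Imaging analysis) sets the collection rule: "Brain MRI will be collected at baseline and in case of CNS toxicity". The Abstract repeats this rule and says that the analysis of the anonymised scans is central, pointing to a Section 9.3.7; the Fazekas, morphometric and radiomic results are then to be related to CNS toxicity. The exploratory objective is "To identify neuroimaging markers (MRI) that are predictive of the occurrence of CNS AEs", in up to 30 patients.

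Two of the baseline readings leave room for judgement:
- Fazekas grade: "We will qualitatively evaluate the presence of White Matter hyperintensities on FLAIR images using a 4-point rating scale".
- In patients with baseline brain metastases, "each of the lesions will be identified and delineated using T1-gadolinium and FLAIR". The resulting tumour and oedema regions give the lesion counts and volumes, and the radiomics analysis reuses them.

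The Central Review text in Section 9.3 covers every scan: "All brain MRIs will be centrally reviewed in Anonymized images with an adequate resolution level". It adds that "the centralized reading will be conducted by central reviewer through a controlled access to the platform". Apart from anonymisation and controlled access, it names only compliance with data-protection rules.

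**The concern.** When a predictor is read by eye, the reader should not know who had the outcome. Here the second scan is requested because the outcome occurred, and it goes to the same review as the baseline scan. Anonymisation hides who the patient is. It does not hide that this patient has a later scan, or why.

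A reader who sees that cue may lean towards the higher grade on a borderline baseline image, or may outline a lesion or its oedema more generously. The lean would fall on patients with CNS AEs, because a toxicity-triggered scan marks a case and never a non-case. At stake is whether an apparent link between baseline white-matter grade, or lesion features, and CNS AEs is a property of the brain or of the reading. With at most 30 patients, a few shifted grades can visibly change the estimate.

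**Working it through.** The protocol gives no figure to reproduce on this point. The check is mainly a comparison of passages, followed by two illustrations of scale.

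**Passages side by side**
1. *Trigger.* Section 9.3 and the Abstract both tie the later MRI to CNS toxicity, which is the outcome of the exploratory objective.
2. *Reader.* The Central Review text sends all brain MRIs to one platform for central reading, so both kinds of scan arrive there.
3. *Safeguards.* Anonymisation, controlled access and data protection are named. Masking to AE status and an order of reading are not.
4. *Timing.* Section 9.2.1 enrols patients 7 to 28 days after lorlatinib starts, and the reporting period in Section 11 opens at the first dose. A CNS AE, and a scan for it, can therefore precede consent. The baseline and toxicity scans could be uploaded together, so the calendar does not guarantee that baseline is read first.
5. *Other documents.* Annex 1 lists no stand-alone documents, so no imaging manual is named. The Abstract refers to a Section 9.3.7 for the central analysis, but the table of contents shows no subsections under 9.3.

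**How many patients**
- CNS AEs: 42% (the CROWN figure in Section 9.5) gives 0.42 × 30 = 12.6. The 55% in the same section gives 0.55 × 30 = 16.5. That is about 13 to 17 of 30.
- Lesion delineation: Section 7 gives 35 patients with baseline brain metastases in the CROWN lorlatinib group and 149 treated. At that share, 35/149 × 30 = 7.0, or about 7 patients. For the others, Fazekas is the main exposed measure.

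**Illustration 1: odds ratio.** Assumed, not from the protocol: 16 patients with and 14 without a CNS AE, and about 30% with Fazekas grade 2 or more in each group (5 and 4 patients).
- No shift: (5/11)/(4/10) = 1.14.
- Two scans upgraded among the cases: (7/9)/(4/10) = 1.94; Fisher p = 0.47.
- Four upgraded: (9/7)/(4/10) = 3.21; Fisher p = 0.16.

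**Illustration 2: false positives.** This is a simulation of 30 patients with no true association, 2,000 runs per setting and a two-sided Mann-Whitney test at 5%. Assumed: Fazekas 0/1/2/3 in 50/30/15/5%. The reader scores one category higher in a given share of the patients whose triggered scan is seen. Each cell gives the rejection rate at 42% / 55% CNS AE incidence.

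| Share upgraded | All cases have a triggered MRI | Half of cases have one |
|---|---|---|
| 0% | 4.5% / 4.3% | 4.0% / 3.6% |
| 20% | 7.7% / 7.4% | 5.4% / 4.3% |
| 30% | 11.3% / 11.2% | 5.4% / 6.5% |
| 50% | 27.5% / 26.2% | 7.3% / 9.2% |

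The Monte Carlo standard error near 5% is √(0.05 × 0.95/2000) ≈ 0.5 percentage points, so small differences in the right-hand column are noise. The result depends heavily on how many cases have a triggered scan and how often the reader leans. The protocol gives neither.

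**The case against.** The strongest reply is that this rests largely on silence. No passage says that the reader sees AE status, compares a patient's scans or rates baseline late, and reading rules can sit in an imaging manual. That is fair as far as it goes: the text shows that the reader could learn the outcome, not that this will happen. But the outcome-triggered scan is a written rule and the protocol already has a Central Review text. Section 9.7 leaves statistical analyses, definitions and scoring to the SAP, which is not the usual home for the release of images to a reader, and no separate imaging document is listed.

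The reply does remove several stronger readings that a reader might infer:
- *That a second MRI is sent only for toxicity.* The text does not say so. One ambiguous Abstract sentence may mean that brain imaging at the first tumour assessment is also collected, and the visit table in Section 9.2 names MRI among the response-assessment methods. If routine follow-up MRIs also reach the platform, a second scan is a weaker cue, although its indication or timing could still give the outcome away.
- *That the scan discloses the outcome for everyone.* Section 9.3 captures only procedures done in routine care, and Section 9.5 says that most CNS AEs are grade 1. Many affected patients may never have a triggered MRI. Nor does the text say whether the reader can link a later scan to the same patient's baseline.
- *That the masks are drawn by hand.* The protocol names software and defines the tumour region by contrast enhancement. Manual drawing is an inference, and the step applies only to patients with baseline brain metastases.
- *That an odds ratio near 3 is to be expected, or that shifted grades decide which marker is reported.* The shifts are invented, neither shifted table is statistically notable, and the protocol sets no reporting threshold.

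**Conclusion.** The point holds in limited form. As written, the collection and reading rules allow a judgement-based baseline rating to be made with a cue to the outcome for some patients. The exposure is clearest for the Fazekas grade, present for lesion and oedema delineation and the radiomics built on it, and smaller for SPM12 volumetry.

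The size of the bias cannot be derived from the protocol. Under the stated assumptions, the false-positive rate ranges from barely changed, when half the cases have a triggered scan and the reader leans seldom, to about 26 to 28%, when every case has one and half are upgraded. These figures show direction only.

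The consequence is confined to one exploratory objective. The primary safety description and the secondary objectives do not depend on it. This is a worthwhile low-priority correction, best made before central reading starts, because masking cannot be restored for images already read with the outcome visible.

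**What to change.** Add to the Central Review text in Section 9.3:
- Each patient's baseline MRI is rated, delineated and locked on the platform before any later MRI of that patient is released to the reviewer.
- The reviewer is masked to CNS AE status and to the indication for each scan.
- Later MRIs are read separately and do not reopen the baseline ratings or masks.

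Correct the Abstract's reference to Section 9.3.7 at the same time, and say whether brain MRIs at the first tumour assessment are collected for all patients in the imaging subset.

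The cost is one paragraph and a platform setting. No extra scan, patient or reader is needed, and clinical care is unchanged. The small downside is that readings must follow a fixed order.
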